DBD	Disruptive Behavior Disorder
DSMB	Data Safety Monitoring Board
DSM-IV-TR	Diagnostic and Statistical Manual of Mental Disorders – Text Revision
ECG	electrocardiogram
EEG	electroencephalogram
EPS	extrapyramidal symptoms
FDA	Food and Drug Administration
GCP	Good Clinical Practice
HR	Heart rate
IAF	Informed Assent Form
ICD-10	International Statistical Classification of Diseases and Health Related Problems 10th Revision
ICF	Informed Consent Form
IQ	intelligence quotient
ICH	International Conference on Harmonization
IRB	Institutional Review Board
ITT	intent to treat
IVRS	Interactive Voice Response System
KBIT-2	Kaufman Brief Intelligence Test, Second Edition
K-SADS-PL	Schedule for Affective Disorders and Schizophrenia for School-aged Children—Present and Lifetime Versions
LNH	Low, normal, high
MedDRA	Medical Dictionary for Regulatory Activities
NCBRF-TIQ	Nisonger Child Behavior Rating Form - Typical Intelligence Quotient
ODD	Oppositional Defiant Disorder
PK	pharmacokinetic

PK-PD	pharmacokinetic-pharmacodynamic
PO	orally
QHS	at bedtime
QTcF	QT corrected using Fridericia's method
RBC	red blood cell
SAE	serious adverse event
SAP	Statistical Analysis Plan
SAS	Simpson-Angus Scale
SM	study medication
SNAP-IV	Swanson, Nolan and Pelham Rating Scale-Revised
SOC	System Organ Class
SOP	Standard Operating Procedure
TDD	Total Daily Dose
TEAE	treatment-emergent adverse event
TEOSS	Treatment of Early Onset Schizophrenia Spectrum Disorders
TESS	Treatment-emergent signs and symptoms
TID	three times per day
US	United States
WBC	white blood cell
WHO-DD	World Health Organization Drug Dictionary

1. INTRODUCTION

The purpose of this statistical analysis plan (SAP) is to reasonably ensure that the tables and data listings which will be produced, and statistical methodologies that will be used, are complete and allow for the arrival at valid conclusions regarding the study objectives. In the development of this SAP, the following documents were used:

- The Final Protocol 810P201 (Amendment 1), Version 2.0, 09-SEP-2008
- Case Report Forms, Version 1.0, 11-MAR-2008.

2. STUDY OBJECTIVES

2.1 PRIMARY OBJECTIVE

The primary objective is to evaluate the safety and tolerability of four doses of SPN-810 in children with ADHD and persistent serious conduct problems.

2.2 SECONDARY OBJECTIVES

- To explore the relationship between SPN-810 plasma concentration exposure and safety and tolerability endpoints.
- To assess the effect of SPN-810 in reducing persistent serious conduct problems as measured by the conduct problem subscale of the Nisonger Child Behavior Rating Form -Typical Intelligence Quotient (NCBRF-TIQ) after 6 weeks of maintenance treatment.

3. DESIGN OF THE STUDY

3.1 STUDY DESIGN

This will be a randomized, multicenter, parallel group, dose-ranging safety and tolerability study in children with ADHD and persistent serious conduct problems. The target subjects are healthy male or female children aged 6 to 12 years, inclusive, with a diagnosis of ADHD with persistent serious conduct problems. To determine eligibility for the study, subjects will undergo an initial screening visit. Seventy-two subjects will be randomized in the study; assuming a 17% dropout rate, it is anticipated that 60 subjects will complete the study.

[figure not shown]
The study will consist of a Screening Period (within 28 days prior to the first dose administration), a Titration Period of 2 to 5 weeks, a Maintenance Period of 6 weeks, and a Safety Follow-up, which will be performed 30 days after the final study visit. The total subject duration in the study will be 16 to 19 weeks depending on the treatment group assignment. The total study duration is anticipated to be 15.5 months.

A total of 72 subjects will be randomized based on weight at baseline, to 1 of 4 treatment groups. A dose titration schedule will be followed (Table 1), where dosing for subjects < 30kg will be initiated at 1.67mg/day and dosing for subjects \geq 30kg or more will be initiated at 3.34mg/day. The titration schedule will be followed until the target dose (Treatment 1, 2, 3, or 4) is reached. Subjects will remain at the target dose for 6 weeks.

Table 1. Dose Titration Schedules (mg/day)

Week	1	2	3	4	5	6
Treatment Weight	Titration	Titration	Titration or Treatment 1	Titration or Treatment 2	Titration or Treatment 3	Treatment 4
< 30kg	1.67 (1.67mg qhs)	3.34 (1.67mg bid)	5 (1.67mg tid)	10 (3.33mg tid)	15 (5mg tid)	20 (6.67mg tid)
≥ 30kg	3.34 (1.67mg bid)	5 (1.67mg tid)	10 (3.33mg tid)	20 (6.67mg tid)	30 (10mg tid)	40 (13.33mg tid)

A study schematic is presented below.

Following 2 weeks of titration, subjects randomized to Treatment 1 in each weight group will receive Maintenance Treatment 1 (5mg/day for children < 30kg and 10mg/day for children ≥ 30kg), while the remaining subjects will receive the same level of drug as a titration step to the next level (Maintenance Treatment 2: 10mg/day and 20mg/day) and so on until the final subjects in each weight group reach the highest doses (20mg/day and 40mg/day).

Subjects will return to the clinic on a weekly basis for a total of 8 to 11 visits following randomization (2 to 5 weeks of titration and 6 weeks of maintenance treatment). Safety,

*Safety Follow-up Phone Visit - 30 days post Final Study Visit

tolerability, and efficacy assessments will be performed at each visit. Blood and urine for clinical laboratory tests will be collected at Screening and at Weeks 2 and 6 of the Maintenance Period.

Blood will be drawn at trough for quantitative PK analysis at Weeks 2 and 3 of the Titration Period. At Week 2 of the Maintenance Period and the Final Visit, the subject's next maintenance dose of Study Medication (SM) will be administered in the clinic. The first PK draw will be a trough sample just prior to dosing. The dose will be administered, and a second draw will be performed between 1 and 3 hours post-dose.

Dose decreases will be permitted during the study for subjects randomized to Treatment 4 only, at the discretion of the Investigator in consultation with the Medical Monitor. Only 1 decrease to the next lowest dose (Treatment 3) will be permitted per subject. Benztropine will be permitted for the treatment of emerging extrapyramidal symptoms (EPS), at a starting dose of 0.5mg BID up to a range of 1 to 4mg/day.

3.1.1 Screening Period

A Screening Period will take place within 28 days prior to the first dose administration to determine subjects' eligibility to participate in the study. Prior to conducting any screening procedures, written informed consent/assent must be obtained from the parent or LAR, and subject (when required).

The NCBRF-TIQ will be administered to determine eligibility. The diagnosis of ADHD will be confirmed with the Schedule for Affective Disorders and Schizophrenia for School-aged Children—Present and Lifetime Versions (K-SADS-PL). The Introductory and Screen Interviews will be completed. The Screen Interview will determine which Supplements should be completed. Supplement 4 (Behavioral Disorders) must be completed to assess ADHD, ODD and CD. If an exclusionary diagnosis is confirmed, the remainder of the diagnostic will not be completed.

Other procedures to be performed will include the collection of medical history and demographic data, physical examination, collection of vital signs, height, and weight, electrocardiogram (ECG), blood collection for hematology and chemistry, urine collection for urinalysis, drug screen, and pregnancy test (for female subjects of menstruating age or ≥ 11 years old). The Kaufman Brief Intelligence Test, Second Edition (KBIT-2) should be administered if an IQ test has not been performed within the past 12 months prior to screening. Concomitant medication and AE information will be collected once informed consent/assent is obtained.

Unscheduled visits may be conducted at the discretion of the investigator throughout all study periods. The medical monitor should be notified promptly of any need for an unscheduled visit.

3.1.2 Titration Period

Subjects who meet the requirements for study participation will proceed to the Titration Period. Randomization will occur at the first Titration Period visit (Baseline). Subjects $< 30\text{kg}$ will be assigned a 1.67mg/day dose (1 week) followed by a 3.34mg/day dose (1 week)

followed by maintenance dosing at 5mg/day or continued titration up to 10, 15 or 20mg/day. Subjects \geq 30kg or more will be assigned a 3.34mg/day dose (1 week) followed by a 5mg/day dose (1 week) followed by maintenance dosing at 10mg/day or continued titration up to 20, 30, or 40mg/day.

Baseline safety (including Simpson-Angus Scale [SAS], Barnes Akathisia Scale [BAS], Abnormal Involuntary Movement Scale [AIMS]) and efficacy assessments (including NCBRF-TIQ, Clinical Global Impression [CGI] and Swanson, Nolan and Pelham Rating Scale - Revised [SNAP-IV]) will be performed. Inclusion/Exclusion criteria should be re-assessed at this visit. Concomitant medication and AE information will be collected.

After the first Titration Period visit, subjects will return to the study site weekly for dose increases, monitoring of AEs, and the administration of safety and efficacy scales. Procedures to be performed are collection of vital signs and weight, and PK blood sampling (at Weeks 2 and 3). Assessments of concomitant medications and drug compliance will be performed.

3.1.3 Maintenance Period

Following dose titration, subjects will be maintained at their designated dose level for 6 weeks. Subjects will return to the study site weekly for monitoring of AEs and the administration of efficacy and safety scales. Procedures to be performed are collection of vital signs and weight at each visit, and blood collection for hematology and chemistry and urine collection for urinalysis (Week 2 only). PK blood sampling will be performed at Week 2 with a first draw at trough drug levels prior to dosing, followed by observed dosing and a second draw 1 to 3 hours post-dose. Assessments of concomitant medications and drug compliance will be performed.

Subjects in the highest dose group (Treatment 4) will be permitted to down titrate once at the Investigator's discretion in consultation with the Medical Monitor. If this down-titration occurs outside a scheduled visit, the subject should be brought into the clinic for evaluation.

For all unscheduled visits, including those unrelated to down-titration, AEs should be documented and vital signs collected. Relevant safety scales should be completed at the discretion of the investigator.

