3.6.7 Other Special Tests for Extrapyramidal Symptoms (EPS)

Simpson-Angus Scale

The Simpson-Angus scale is a 10-item rating scale that is widely used for assessment of neuroleptic-induced Parkinsonism. It consists of 1 item measuring gait, 6 items measuring rigidity, and three items measuring glabella tap, tremor and salivation, respectively. This assessment will be administered at all post-screening study visits.

Barnes Akathisia Scale

The Barnes Akathisia scale is a rating scale for drug-induced akathisia and includes components for rating the observable, restless movements characteristic of akathisia, the awareness of restlessness, and any distress associated with the condition. This assessment will be administered at all post-screening study visits.

Abnormal Involuntary Movement Scale (AIMS)

The AIMS test is a rating scale used to measure tardive dyskinesia. There are 12 items that rate involuntary movements of various areas of the subject's body. This assessment will be administered at all post-screening study visits.

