6.7 OTHER SAFETY ANALYSES FOR EXTRAPYRAMIDAL SYMPTOMS (EPS)

6.7.1 Simpson-Angus Scale (SAS)

Listing 6.7.1.1 provides subject-wise SAS scores for each visit. The occurrence of neurological side effects will be assessed by looking at the changes in scores from baseline to post-baseline visits.

For each item on the SAS scale, the number (and percentage) of subjects with a worse score at any post-baseline visit, compared to baseline, will be presented in Table 6.7.1.1.

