6.7.2 Barnes Akathisia Scale (BAS)

Listing 6.7.2.1 provides subject-wise BAS scores for each visit. The occurrence of neurological side effects will be assessed by looking at the changes in scores from baseline to post-baseline visits.

For each item on the BAS scale, the number (and percentage) of subjects with a worse score at any post-baseline visit, compared to baseline, will be presented in Table 6.7.2.1.

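### EPS scales are optional at unscheduled visits, and unscheduled data stay out of summaries, so EPS that comes and goes between scheduled ratings can be counted as not worse

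*SAP*

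**What the plan says.** All references are to the SAP.

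- **Unscheduled visits.** Section 3.1.1 allows them in every study period. On their content, section 3.1.3 states "For all unscheduled visits, including those unrelated to down-titration, AEs should be documented and vital signs collected", followed by "Relevant safety scales should be completed at the discretion of the investigator".
- **Dose reduction.** Section 3.1 allows it in Treatment 4 only: "Only 1 decrease to the next lowest dose (Treatment 3) will be permitted per subject". Section 3.1.3 adds: "If this down-titration occurs outside a scheduled visit, the subject should be brought into the clinic for evaluation".
- **Benztropine.** Section 3.1 permits it for emerging EPS and does not restrict it to one arm.
- **Scale schedule.** Section 3.6.7 says of each of SAS, BAS and AIMS: "This assessment will be administered at all post-screening study visits".
- **EPS tables.** Section 6.7.1 specifies, for each SAS item, "the number (and percentage) of subjects with a worse score at any post-baseline visit, compared to baseline, will be presented in Table 6.7.1.1". Sections 6.7.2 and 6.7.3 use the same rule for BAS and AIMS in Tables 6.7.2.1 and 6.7.3.1. None of the three says what to do when a rating is missing.
- **Unscheduled data.** Section 4 sends them to the listings and keeps them out of the summaries. It also keeps every child randomized to Treatment 4 in that group, reduced or not.

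**The concern.** The tables in section 6.7 can count only what was rated and then summarized. Two rules stand between an EPS event seen at an unscheduled visit and its place in those tables. The investigator may leave the scales undone (section 3.1.3), and a rating that is done may be dropped because the visit was unscheduled (section 4).

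The visits at risk are those where a child is seen because something has gone wrong. If the dose is then lowered or benztropine is given, the next scheduled rating describes a changed state. A child who is back to baseline on an item by then, and who had no worse score on it at any other scheduled rating, enters the table as not worse.

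The primary objective is the safety and tolerability of four doses (section 2.1), and SAS, BAS and AIMS are the named neurological measures (section 3.6). One route to a missed rating, the dose reduction, exists in the top-dose arm only, so the loss need not be equal across arms.

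**Working it through.** **1. Arm size.** Section 3.2 gives 72 randomized, 17% dropout and 60 completers. Check: 72 × (1 − 0.17) = 59.76, about 60, so the plan's figure reproduces. With 1:1:1:1 allocation (section 3.3), 72/4 = 18 randomized and 60/4 = 15 completers per arm. The safety population needs one dose, so 18 is the natural approximate denominator.

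**2. Time between required ratings.** Maintenance visits are weekly with a window of ±2 days (section 3.4). The longest gap within the windows is 7 + 2 + 2 = 11 days.

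**3. The rules side by side.**

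| Question | One place | Another place |
|---|---|---|
| Are the scales required at an unscheduled visit? | 3.1.3: no, investigator's choice | 3.6.7: every study visit after screening |
| Does an unscheduled rating count? | 4: listed only | 6.7.1–6.7.3: worse at any visit after baseline |

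Under the reading that loses most information, the scales are not done. Under the intermediate reading they are done, listed and left out. Only if sections 3.6.7 and 6.7 override sections 3.1.3 and 4 is the event both rated and counted. The SAP does not say which prevails.

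**4. Routes to a missed event, by arm.**

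| Route | Treatments 1–3 | Treatment 4 |
|---|---|---|
| Unscheduled visit, benztropine, unrated | possible | possible |
| Unscheduled visit, dose reduction, unrated | not allowed | possible |
| Discontinuation | Final Visit includes the scales | Final Visit includes the scales |

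Only the second row differs between arms.

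**5. Size.** If *m* children in an arm of *n* are wrongly counted as not worse on an item, the percentage is low by 100 × *m*/*n*. The SAP gives no value for *m*; the range 0 to 4 is an assumption.

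| *m* | *n* = 18 | *n* = 15 |
|---|---|---|
| 0 | 0 | 0 |
| 1 | 5.6 | 6.7 |
| 2 | 11.1 | 13.3 |
| 3 | 16.7 | 20.0 |
| 4 | 22.2 | 26.7 |

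As an illustration, suppose 4 of 18 children truly worsened (22.2%). Missing 1, 2 or 3 of them would show 16.7%, 11.1% or 5.6%.

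**The case against.** **The event is recorded elsewhere.** This stands. AEs must be documented at the unscheduled visit and enter the AE tables by preferred term, severity and relationship (section 6.1.1). AEs leading to dose reduction are listed (section 6.1.3), reduced children are counted in Table 4.4.2, and benztropine use would appear in Table 6.6.1. The loss is confined to the item-level EPS tables, which an AE record cannot fill.

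**Several things must coincide.** This also stands. The symptom must arise between scheduled visits, be unrated or excluded, return to baseline by the next scheduled rating, and never be worse on that item at any other scheduled rating. That is why the range must start at 0.

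**The scales may already be done.** Section 3.1.3 points investigators to the relevant scales, and most may complete them. That helps only if the ratings are then counted, which section 4 puts in doubt.

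**Sections 3.6.7 and 3.1.3 may be compatible.** If study visits in section 3.6.7 means scheduled visits, the two do not clash. The gap at unscheduled visits then remains, and so does the conflict between sections 4 and 6.7.

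**Stronger readings that a reader might infer.**

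- *Only Treatment 4 is under-ascertained.* Unscheduled visits without ratings, and benztropine, are possible in every arm. Only the dose-reduction route is specific to Treatment 4.
- *EPS is what limits the top dose.* The SAP gives no reason for reductions beyond the investigator's discretion in consultation with the Medical Monitor.
- *The tables will flatten or reverse the dose relation.* Treatment 4 has up to 11 visits after randomization against 8 for Treatment 1 (section 3.1). It therefore has more scheduled chances to be counted worse, which pulls the other way.

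**Conclusion.** The concern holds as a conflict between stated rules that can give a wrong count in Tables 6.7.1.1, 6.7.2.1 and 6.7.3.1 in any arm. Each miscounted child costs about 5.6 percentage points on an item, and 0 to 4 children would cost 0 to 22 points. These figures rest on 18 per arm and on an assumed number of children that the SAP does not supply.

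Because the dose-reduction route exists in Treatment 4 only, the comparison of EPS across doses can be biased. The documents do not establish the net direction, and they do not support a claim that the top dose will look better than it is. The point applies only to events seen between scheduled visits, since the scales are required at scheduled ones. It assumes that section 4's rule keeping reduced children in Treatment 4 also governs the safety tables.

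It should be settled before ratings are collected, because a rating not made at the time cannot be recovered at analysis.

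**What to change.** 1. Reconcile sections 3.1.3 and 3.6.7. Require SAS, BAS and AIMS at every unscheduled visit made for a dose reduction or for suspected EPS, in all arms. A requirement in Treatment 4 only would add counted ratings to one arm and create an asymmetry of its own.
2. Record the time of each such rating relative to any dose change or first benztropine dose. Section 3.1.3 does not say that the clinic evaluation comes before the reduction, so a rating made before the change cannot be assumed.
3. State in sections 6.7.1 to 6.7.3, as an explicit exception to section 4, that unscheduled ratings after baseline count in the three tables.
4. Add a sensitivity version of each table restricted to scheduled visits, so that the effect of the extra ratings is visible by arm.

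The cost is a few minutes per unscheduled visit, a schedule footnote or short amendment, and one extra display per scale. The rules on when a dose is reduced or benztropine is given are not changed.

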3.1.4 Final Visit/Early Termination

Subjects will return to the study site for a final visit, after completing the 6-week Maintenance Period, or prior to early discontinuation. AEs will be monitored and safety and efficacy scales will be administered. The procedures to be performed will include physical examination, collection of vital signs, height, and weight, ECG, blood collection for hematology and chemistry, urine collection for urinalysis, drug screen, and pregnancy test (for female subjects of menstruating age or \geq 11 years old). PK blood sampling will be performed, with a first draw at trough drug levels prior to dosing, followed by observed dosing and a second draw 1 to 3 hours post-dose. Assessments of concomitant medications and drug compliance will be performed.

3.1.5 Post-Study Follow-up Visit

The post-study Follow-up visit will consist of a phone call to each subject 30 days after the final visit. New non-serious AEs that started within 7 days after the subject's last dose will be collected. All new SAEs will be collected, and reported if the event is at least possibly related to SM. AEs or SAEs that are ongoing at the subject's last study visit must be followed until resolution or if, in the medical judgment of the Investigator, the event has stabilized or is assessed as chronic.

3.2 SAMPLE SIZE CONSIDERATION

Seventy-two subjects will be randomized in the study. Assuming a 17% dropout rate, it is anticipated that 60 subjects will complete the study. The sample size is not based on any statistical considerations, but it was judged adequate to provide safety, PK, and efficacy information for a proof-of-concept study.

3.3 RANDOMIZATION PROCEDURE

The randomization for this study will be managed centrally by an IVRS vendor; specific instructions to conduct subject randomization will be provided in a separate document to all investigational sites, along with site staff access to the system.

A randomization scheme will be generated using a pseudo-random number generator in a computer program. The method avoids bias by use of a chance mechanism. Within each weight group, the randomization scheme assigns Treatment 1, Treatment 2, Treatment 3, or Treatment 4 to each randomization number in a 1:1:1:1 ratio.

Upon admission to the study, subjects will be assigned a 4-digit screening number, in the order that they are entered. Subjects who subsequently meet all eligibility criteria will be assigned a 6-digit randomization number. The first 3 digits will refer to the site, and the last 3 will refer to the subject-specific number, which will be assigned according to the randomization scheme.

Once a randomization number has been assigned, no attempt should be made to use that number again, if, for example, a subject is withdrawn. All subjects are randomized only once.

3.4 SCHEDULE OF VISITS AND PROCEDURE

All subjects who are randomized and take any SM will be followed according to the protocol, unless consent for follow-up is withdrawn. The Sponsor, or the Sponsor's designee, must be notified of all deviations from the protocol visits or procedures and these procedures, if applicable, will be rescheduled or performed at the nearest possible time to the original schedule.

The exhibit on the next page presents the schedule of visits and procedures for the study.

Exhibit: Schedule of Visits and Procedures

PERIOD	Screening	Titration					Maintenance					Final Visit ^k	Follow-up	
		1	2	3 ^b	4 ^c	5 ^d	6	7	8	9	10	11		
VISIT	0													
WEEK	0	1	2	3 ^b	4 ^c	5 ^d	1	2	3	4	5	6	7	
WINDOW (DAYS)	Within 28 days prior to dosing	± 1	± 1	± 1	± 1	± 1	± 2	± 2	± 2	± 2	± 2	± 2	± 3	
Informed Consent/Assent ^a	X													
IVRS Call	X	X											X	
K-SADS-PL	X													
IQ Test (KBIT-2) ^e	X													
Inclusion/Exclusion Criteria	X	X												
Randomization		X												
Medical History	X													
Demographics	X													
Physical Examination	X												X	
ECG (12-lead)	X												X	
Vital Signs, height, and weight ^f	X	X	X	X	X	X	X	X	X	X	X	X	X	
Hematology/chemistry	X							X					X	
Urinalysis	X							X					X	
PK Blood Sampling			X	X					X ⁱ				X ⁱ	
Urine Drug Screen	X												X	
Urine Pregnancy Test ^g	X												X	
Efficacy Scales (NCBRF-TIQ, CGI, SNAP-IV)	X ^h	X	X	X	X	X	X	X	X	X	X	X	X	
Safety Scales (Simpson-Angus, Barnes, AIMS)		X	X	X	X	X	X	X	X	X	X	X	X	
Adverse Events	X ^j	X	X	X	X	X	X	X	X	X	X	X	X	X ^l
Concomitant Medications	X	X	X	X	X	X	X	X	X	X	X	X	X	
Drug Return and Compliance			X	X	X	X	X	X	X	X	X	X	X	
Drug Dispensation			X	X	X	X	X	X	X	X	X	X	X	

CONFIDENTIAL MATERIAL

This material is the property of Supernus[®] Pharmaceuticals, Inc.
and must not be disclosed or used except as authorized in writing by Supernus[®] Pharmaceuticals, Inc.

- a Written consent must be obtained prior to performing any study-related procedure.
- b For subjects receiving Treatments 2, 3 and 4 only.
- c For subjects receiving Treatment 3 and 4 only.
- d For subjects receiving Treatment 4 only.
- e IQ test to be administered if not performed 12 months prior to screening.
- f Heart rate (HR), blood pressure, temperature, respiratory rate, and weight will be measured weekly. Height will only be measured at Screening and Final Visit.
- g To be performed for female subjects of menstruating age or \geq 11 years old.
- h Only NCBRF-TIQ will be performed at screening for purposes of assessing eligibility.
- i First draw at trough, then the subject's next maintenance dose is observed in clinic between 1 and 3 hours prior to blood draw for second PK sample. PK sample not drawn at early termination if subject is discontinuing drug for safety or tolerability reasons.
- j AEs and SAEs will be followed from the time that the subject signs the ICF.
- k To be performed at the end of Maintenance Period or prior to early discontinuation.
- l There will be a phone call to each subject 30 days after the final visit. New non-serious AEs that started within 7 days after the last dose will be collected. New SAEs will be collected, and reported if at least possibly related to SM. AEs or SAEs that are ongoing at the last study visit must be followed until resolution, stabilization, or assessed as chronic.

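### Footnote i withholds the early-termination PK sample from children stopping for safety or tolerability, section 3.1.4 requires it, and the exposure-safety objective is weakened, mainly for those stopping before Maintenance Week 2

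*SAP*

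**What the plan says.** The first secondary objective (SAP 2.2) is "To explore the relationship between SPN-810 plasma concentration exposure and safety and tolerability endpoints".

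PK blood is scheduled at three stages:

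- Titration (SAP 3.1): "Blood will be drawn at trough for quantitative PK analysis at Weeks 2 and 3 of the Titration Period". The Titration Week 3 visit is marked "For subjects receiving Treatments 2, 3 and 4 only", so Treatment 1 has one titration trough and the other arms have two.
- Maintenance (SAP 3.1.3): "PK blood sampling will be performed at Week 2 with a first draw at trough drug levels prior to dosing". An observed dose and a draw 1 to 3 hours later complete the pair.
- Final Visit/Early Termination (SAP 3.1.4): "PK blood sampling will be performed, with a first draw at trough drug levels prior to dosing, followed by observed dosing and a second draw". The timing of that later draw is the same as at Maintenance Week 2. One visit serves both completers and early stoppers: "Subjects will return to the study site for a final visit, after completing the 6-week Maintenance Period, or prior to early discontinuation".

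Footnote i in SAP 3.4 is attached to the PK mark for that last visit and adds an exception: "PK sample not drawn at early termination if subject is discontinuing drug for safety or tolerability reasons". It does not separate the trough from the post-dose draw.

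The PK population (SAP 4.1) needs only one PK measurement at any time. SAP sections 5 and 6 describe no exposure-safety analysis and no handling of missing concentrations.

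**The concern.** Two passages about one visit give different instructions. Section 3.1.4 samples every child; footnote i leaves out those who stop for safety or tolerability.

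The exception also depends on the outcome that the objective studies. A child who leaves for an administrative reason gives a concentration at the stop; a child who leaves because the drug was not tolerated does not. The missing value is the one closest in time and dose to the event, so the missingness is informative. What remains for such a child depends on the time of the stop. If it comes before Maintenance Week 2, only titration troughs at low doses are left, and pairing those with the event would understate the exposure at which it occurred.

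**Working it through.** **1. How many children the rule can reach.** Inputs from SAP 3.2: 72 randomized, 17% dropout, 60 completers.

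- Stated figure: 72 × (1 − 0.17) = 59.76, which rounds to 60. It reproduces.
- Implied dropouts: 72 − 60 = 12 (12/72 = 16.7%).
- The SAP gives no split by reason. If 25%, 50%, 75% or 100% of the 12 stop for safety or tolerability, the rule reaches 3, 6, 9 or 12 children (4.2% to 16.7% of 72).

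**2. Draws planned and draws kept.** A completer has 1 titration draw (Treatment 1) or 2 (Treatments 2-4), plus 2 at Maintenance Week 2 and 2 at the Final Visit: 5 or 6 in all. Under footnote i a child stopping for safety keeps:

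- none, if stopping before Titration Week 2;
- 1-2 troughs, if stopping between then and Maintenance Week 2;
- 3-4 draws, including the trough/post-dose pair at the maintenance dose, if stopping later.

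**3. Width of the gap.** Baseline is the Titration Week 1 visit and visits are weekly, so the Titration Week 2 and 3 visits fall at about days 7 and 14. Troughs taken there reflect the doses of study weeks 1 and 2. Doses are from Table 1. Each ratio is the dose in force divided by the dose at the last titration trough, one per weekly step up to Maintenance Week 2.

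| Arm | No scheduled draw, about | First target-dose sample, share of planned weeks | Ratios, ≥ 30 kg | Ratios, < 30 kg |
|---|---|---|---|---|
| 1 | day 7 to 21 | 3/8 = 38% | 1.5, 3.0 | 2.0, 3.0 |
| 2 | day 14 to 28 | 4/9 = 44% | 2, 4 | 1.5, 3.0 |
| 3 | day 14 to 35 | 5/10 = 50% | 2, 4, 6 | 1.5, 3.0, 4.5 |
| 4 | day 14 to 42 | 6/11 = 55% | 2, 4, 6, 8 | 1.5, 3.0, 4.5, 6.0 |

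For Treatment 4, 30 kg or more, the last trough is at 5 mg/day: 10/5 = 2, 20/5 = 4, 30/5 = 6, 40/5 = 8. Under 30 kg it is at 3.34 mg/day: 5/3.34 = 1.5, 10/3.34 = 3.0, 15/3.34 = 4.5, 20/3.34 = 6.0. If the troughs were instead taken at the end of the named weeks, the last one would be at 10 or 5 mg/day, and the largest Treatment 4 ratio would be 40/10 = 20/5 = 4.

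**4. What the gap does to an exposure-safety slope.** The SAP gives no inputs, so these are assumptions: 72 children on the Table 1 doses, weekly stopping risk with slope 1 on log exposure, between-child log SD 0.5, and about 8-12 tolerability stops, with footnote i in force. That number of stops is 67-100% of the 12 implied dropouts, the upper part of the range in step 1.

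| Exposure used | Median slope | Wrong sign |
|---|---|---|
| True exposure at the stop | 0.70 to 0.90 | 4-11% of trials |
| Last observed concentration | −0.12 to 0.12 | 41-56% |
| Earlier samples scaled to the dose in force, PK dose-proportional (about 10 stops) | 0.88 | 6% |

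The ranges cover the settings tried. In the setting that gave 0.88 for scaled exposure, true exposure gave 0.85 with 8% wrong sign. With residual log SD 0.5 instead of 0.25, both gave 0.70. About 65% of stops came after Maintenance Week 2, and on average about 0.2 children per trial had no PK sample at all.

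Applying the remaining 35% to step 1 gives 0.35 × 3 ≈ 1 to 0.35 × 12 ≈ 4 children left with at most titration troughs.

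**The case against.** - **Footnote i can be read as a specific exception to a general statement, leaving only a cross-reference missing.** That reading is possible. But 3.1.4 covers early termination expressly and gives no exception, so a reader of that section alone would expect the sample. Reading them together also leaves the outcome-dependent gap in place.
- **Earlier samples serve most of these children.** This stands for anyone stopping after Maintenance Week 2, who already has a pair at the maintenance dose. A reader might infer that children stopping for safety drop out of the PK data; the one-measurement definition of the PK population does not support that.
- **Safety information is wider than discontinuation.** This stands. A reader might infer that the rule removes exactly the children who show the safety signal. Adverse events and the three neurological scales are collected at each post-baseline visit, and children with events who continue, receive benztropine or step down from Treatment 4 are still sampled.
- **The bias belongs to an analysis that the SAP does not plan.** This stands as to size. A reader might infer that the exposure-safety relation will be flattened or reversed. The documents do not support that, because no last-observed-concentration analysis is specified, and a protocol or PK plan not shown may hold a model-based one. Scaling by dose does not close the point, however: it assumes proportionality and cannot reveal an unusual concentration at the event.
- **The 8-fold figure is an extreme.** This stands. It applies to Treatment 4 children of 30 kg or more in about the last week of the gap.
- **Sampling schedules belong to the protocol.** True in general, but this SAP restates the schedule and does so in two conflicting ways.

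**Conclusion.** The point holds in a limited form. Sections 3.1.4 and 3.4 conflict on whether children stopping for safety or tolerability give a PK sample. Under footnote i the concentration nearest the event is informatively missing, which weakens a stated secondary objective without defeating it.

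The rule reaches about 3 to 12 of 72 children, assuming that 25-100% of the 12 implied dropouts are for safety. The serious loss falls on those stopping before Maintenance Week 2, perhaps 1 to 4 under the simulated timing, and above all in Treatments 3 and 4. The dose ratios assume weekly visits on schedule and troughs taken before the step-up. No single bias figure can be given, because its size turns on the unspecified analysis and on whether PK is dose-proportional. The objective is exploratory and the sample size has no statistical basis, so this is a change worth making for its low cost and not a threat to the trial's main conclusions.

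**What to change.** Reconcile footnote i with 3.1.4 so that both state that a child stopping for safety or tolerability gives a single PK tube with the hematology/chemistry blood already drawn at the early-termination visit. Record the date and time of the last dose taken, and state that the sample requires no dose. Whether any dose is given at that visit is for the sponsor to reconcile.

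In the exposure-safety analysis, wherever it is specified, use measured or modelled exposure at the dose in force when the event occurred, not the last available concentration. If earlier samples are scaled by dose, state the proportionality assumption.

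The cost is one extra tube at a planned venipuncture, last-dose date and time on the CRF, and matching edits to two passages. The downside is that some samples will fall at irregular times after the last dose, so the analysis has to use the recorded times and cannot treat them as troughs.
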